4.3.3.2. Rationale for Virologic Response-Driven BCV Treatment Duration

Because of the observed toxicities associated with BCV therapy (primarily GI/diarrhea and elevations in liver enzymes), there is the recognized need to balance potential side effects against potential therapeutic benefit of BCV therapy. Because of the rapid virologic response to BCV, a shorter course of BCV may be adequate for the treatment of AdV, while minimizing the risk of GI AEs. Therefore, subjects randomized to BCV in this study will be managed according to a virologic response-driven approach, in which BCV therapy is administered until AdV plasma viremia is confirmed to be undetectable, up to a maximum of 16 weeks, contingent on their not meeting pre-defined tolerability thresholds requiring interruption or discontinuation of treatment (Section 8.3).

A virologic response-driven approach for BCV is supported by the rapid antiviral response observed in clinical trials. In Study CMX001-304, subjects treated with BCV overall demonstrated rapid declines in AdV plasma viremia, typically after 1 to 4 weeks of therapy with a median time to undetectable AdV viremia of 12 to 22 days among pediatric subjects; clearance of AdV respiratory secretions and urine as well as plasma was seen in the majority of subjects after 4 weeks of BCV. Pediatric subjects with lower AdV viral loads at baseline (< 10,000 copies/mL) cleared within a median 8 days of BCV initiation. Among pediatric

subjects with AdV DNA $< 5 \log_{10}$ ($< 100,000$ copies/mL), 72% cleared within 4 weeks (Prasad 2017). Furthermore, subjects with an early virologic response had better outcomes (data presented in Section 4.3.7). Similar rapid virologic responses were observed with BCV among patients treated in the expanded access setting (Florescu 2012, Hiwarkar 2017).

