7.1. Subject Inclusion Criteria

Subject must meet all of the following criteria, as applicable, to be eligible for participation in this study:

1. Aged at least 2 months and less than 18-years-old on Day 1
2. Have received a T cell-depleted allogeneic (i.e., non-autologous) HCT within the previous 100 days, where "T cell-depleted" describes EITHER:
 - ex vivo T cell depletion via positive selection (e.g., CD34+ cell) or negative selection (e.g., T cell receptor α/β or CD3+ cell removal by column filtration), OR
 - serotherapy with ATG (cumulative dose of ≥ 3 mg/kg rabbit-derived ATG or ≥ 50 mg/kg of equine-derived ATG) administered within 10 days prior to transplant or at any time post-transplant and prior to Day 1 OR
 - serotherapy with alemtuzumab administered within 30 days prior to transplant or at any time post-transplant and prior to Day 1

3. First detectable AdV DNA plasma viremia since the qualifying transplant occurred within 21 days prior to Day 1
4. AdV DNA plasma viremia ≥ 1000 copies/mL and rising, defined as two consecutive results ≥ 1000 copies/mL from the designated central virology laboratory, with the second result being greater than the first. The second sample must be drawn at least 48 hours after the first sample and no more than 7 days prior to Day 1
5. If male of reproductive potential, willing to use an acceptable contraceptive method(s) throughout the duration of his participation in the study and until 90 days following last dose of BCV when engaging in sexual intercourse with a female partner of childbearing potential
6. If female of child-bearing potential (i.e., post menarche and not surgically sterilized), willing to use two acceptable contraceptive methods, one of which must be a barrier method, throughout the duration of her participation in the study and until 90 days following last dose of BCV when engaging in sexual intercourse with a non-sterile male
7. Able to provide written informed consent or assent, with legal guardian consent, as required by applicable local or national law and institutional practice, based on the age of the subject
8. Available to participate in all required study activities for the entire duration of the study (i.e., inclusive of the Week 36 assessment)

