8.8. Randomization and Blinding

All treatments will be administered under open-label conditions.

Subjects who meet all applicable eligibility criteria will be randomized to one of two treatment arms (BCV or SoC) in a 2:1 ratio using an automated IV/WRS. During randomization, subjects will be stratified based on the following variables:

- last (non-baseline) screening AdV viremia ($\geq 10,000$ copies/mL vs. $< 10,000$ copies/mL)
- time from transplant to randomization (≥ 28 days vs. < 28 days), and
- T cell-depletion methodology (receipt of alemtuzumab or ex vivo depletion vs. receipt of ATG)

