10.1. Virologic Evaluations and Sample Collection

Blood (plasma), urine, stool, and respiratory secretions, and other samples/specimens for virologic evaluations will be collected at screening, on Day 1 (before randomization), and at periodic intervals throughout the treatment and post-treatment periods of the study as follows:

- Blood will be collected during screening, on Day 1 (before randomization), and at each subsequent assessment for real-time analysis of AdV viremia in plasma at the designated central virology laboratory. These samples will also be analyzed in real time for CMV viremia. The Day 1 (baseline) samples will also be analyzed for BKV viremia. The testing for BKV viremia will not be performed in real-time and the results will not be reported to the sites.
- Urine, stool (where available), and respiratory secretions (nasopharyngeal swab and bronchoalveolar lavage, if appropriate, based on symptoms) will be collected from all subjects on Day 1 (before randomization) and at Weeks 4, 6, 8, 12, and 16. Samples will also be collected from subjects: (1) at the same time that AdV viremia is confirmed as undetectable (i.e., at the time the confirmatory plasma sample is drawn), or (2) if BCV is re-initiated after the recurrence of AdV viremia ≥ 1000 copies/mL (with the samples collected prior to re-initiation of BCV), as applicable. Samples may also be collected at any time on the basis of signs or symptoms suggestive of AdV disease. Based on the clinical status of the subject, in consultation with the Chimerix Medical Monitor (or designee), investigators may request real time analysis of some or all non-plasma specimens for AdV viral load.
- While subjects are inpatient and, where practicable, once subjects are outpatient, stool samples will be collected on Day 1 (before randomization) and each subsequent assessment during treatment and follow-up and stored for possible virologic analyses (e.g., additional AdV or other dsDNA virus viral load analyses, analyses for other viruses, viral genotypic and/or phenotypic assessments).

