12.4. Efficacy Analyses

12.4.1. Primary Efficacy Endpoint

The primary AAUC analysis will utilize all randomized subjects (ITT) in an analysis of covariance (ANCOVA) with all stratification factors included in the model: T cell-depletion method (alemtuzumab or ex vivo cell selection vs. ATG), time from HCT to randomization (< 28 days vs. \geq 28 days), and baseline AdV viremia (continuous \log_{10} copies/mL). These stratification factors have been selected as those that are clearly related to time to immune reconstitution (time from HCT to confirmed AdV viremia > 1000 copies/mL and thus randomization, procedural differences in depth and duration of immune suppression by T cell-depletion method) with resulting expected differences in clearance of viremia, and/or association with mortality (peak viral load). Regarding baseline AdV viremia, subjects will be stratified at the time of randomization according to \geq 10,000 vs. < 10,000 copies/mL; however, this factor will be included in the analysis as a continuous covariate in order to improve power in determining a treatment effect. In the ANCOVA, AdV viremia values that are undetectable will be imputed at 99 copies/mL (i.e., one less than the lower limit of detection of 100 copies/mL) and values that are detected, but not quantifiable (BLQ) will be imputed at 189 copies/mL (i.e., one less than the lower limit of quantification of 190 copies/mL).

Subjects who die or are lost to follow-up (i.e., drop-outs) prior to Week 16 are accounted for inherently in the AAUC approach by truncating their follow-up period, thereby normalizing AUC over time of follow-up (Li 2012). It should be noted that subjects lost to follow-up are anticipated to be zero or negligible, and approximately 16% to 24% of subjects are expected to die by Week 16. Regardless, the primary analysis will be supplemented by a number of planned sensitivity analyses to assess the impact of subjects who die prior to Week 16 and other potential influential elements on the primary inference and to allow for a more comprehensive assessment of efficacy.

The first three approaches are proposed to account for these subjects in a typical missing data framework:

- Jump to reference imputation, where the missing part of the trajectory is imputed from the control group average ([Kenward 2015](#)).

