12.4.2. Secondary Efficacy Endpoints

Continuous secondary efficacy analyses will use the same method used for the primary analysis.

Dichotomous secondary efficacy analyses will be analyzed using a Cochran-Mantel-Haenszel test stratified by each of the stratification factors. Number of failures and failure rates will be presented for each treatment arm. Cochran-Mantel-Haenszel p-values, estimated common odds ratios, and corresponding approximate 95% CIs will be presented for each comparison. The Breslow-Day test will be used to test the homogeneity of the odds ratios. Missing data will be imputed as failure.

Most time-to-event analyses will be performed using Kaplan-Meier methods/plots and Cox models. P-values and hazard ratios along with their 95% CIs will be presented for each treatment comparison. Missing data will be censored, generally at the earlier of the end of study for each subject or the time point for the specific analysis.

Non-relapse mortality will be analyzed with relapse as a competing risk adjusted for baseline strata, with corresponding cumulative incidence plots, Fine-Gray models, and cause-specific and sub-distribution hazard ratios with corresponding 95% CIs.

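### Section 12.4.1 names baseline viremia as the stratifier although randomization uses a screening value, and the virologic responder tests use viremia at only two levels, at a modest cost in power

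*Combined protocol and SAP*

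**What the plan says.** Randomization (section 8.8, and likewise the synopsis and section 6.1) has three two-level factors: time from transplant, T cell-depletion method, and "last (non-baseline) screening AdV viremia" split at 10,000 copies/mL.

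Section 12.4.1 describes the primary model as an "analysis of covariance (ANCOVA) with all stratification factors included in the model" and lists continuous log10 baseline viremia as one of those factors, as does the synopsis. Section 12.4.1 goes on: "Regarding baseline AdV viremia, subjects will be stratified at the time of randomization according to" the 10,000 cut, and explains that "this factor will be included in the analysis as a continuous covariate in order to improve power in determining a treatment effect".

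Baseline means the Day 1 sample. Section 10.1 equates the two: "The Day 1 (baseline) samples will also be analyzed for BKV viremia". The second qualifying screening sample is a different draw. Section 7.1 says: "The second sample must be drawn at least 48 hours after the first sample and no more than 7 days prior to Day 1".

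For responder endpoints, section 12.4.2 says: "Dichotomous secondary efficacy analyses will be analyzed using a Cochran-Mantel-Haenszel test stratified by each of the stratification factors". Continuous secondary endpoints keep the primary method. The pairwise comparisons in 12.4.1 are made within stratum, and 12.9 takes the stratification factors as subgroups. None of these places says which viremia value defines the stratum.

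**The concern.** There are two linked problems.

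The first is a contradiction in the text. Section 12.4.1 treats the ANCOVA covariate and the randomization factor as one variable measured on two scales. They come from different samples, up to 7 days apart, in children enrolled because their virus is rising. A programmer asked to stratify by the stratification factors could use the randomization-system value or could cut the Day 1 value at 10,000. In an open-label trial whose SAP may be amended until database lock (section 12), that choice should be closed early.

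The second is efficiency. The plan's reason for using continuous viremia in the primary analysis applies equally to whether a child becomes undetectable or falls by 1 or 2 log10. CMH cannot take a continuous covariate, so a child at 10^4 copies/mL and one at 10^7 share a viremia level. The protocol's own background suggests that starting load matters: children below 10,000 copies/mL "cleared within a median 8 days of BCV initiation" (section 4.3.3.2). The power of several early virologic endpoints is at stake. Neither the validity of the tests nor the primary analysis is.

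**Working it through.** **The plan's own figure.** Section 12.1 gives more than 90% power for AAUC with difference 0.6, SD 1.03 and 94:47 subjects. SE = 1.03 × √(1/47 + 1/94) = 0.184; 0.6/0.184 = 3.26; power = Φ(3.26 − 1.96) = 90.3% (89.9% with the noncentral t). Two-sided 0.05 is an assumption. The figure reproduces. No power is stated for the responder endpoints.

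**Strata.** Crossing three two-level factors gives 2 × 2 × 2 = 8 strata, on average 47/8 ≈ 6 SoC and 94/8 ≈ 12 BCV subjects each.

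**Simulation.** From the documents: 141 subjects, 2:1, stratified randomization, cut at 4 log10. Assumed: screening log10 viremia = 3 + gamma(shape 2, scale 0.6); Day 1 = screening + normal rise; the other two factors present in 50% and 30%; log-odds of response linear in Day 1 viremia with slope c per log10; treatment log odds ratio 1.05 to 1.4. There were 4,000 trials per row, so the Monte Carlo error near 85% power is √(0.85 × 0.15/4000) ≈ 0.6 points. Entries are power in %; the gain is the logistic column with continuous Day 1 viremia minus CMH on screening strata.

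| c | Rise (SD) | Response BCV / SoC | CMH, screening strata | CMH, Day 1 strata | Logistic, two-level screening | Logistic, continuous Day 1 | Gain |
|---|---|---|---|---|---|---|---|
| 0.5 | 0.2 (0.3) | 63.6 / 39.0 | 80.6 | 80.4 | 81.4 | 82.4 | 1.8 |
| 0.5 | 0.4 (0.5) | 61.3 / 36.9 | 78.7 | 77.7 | 79.6 | 80.6 | 1.9 |
| 1.0 | 0.2 (0.3) | 65.4 / 40.1 | 84.3 | 83.8 | 85.0 | 87.0 | 2.7 |
| 1.0 | 0.4 (0.5) | 61.0 / 36.3 | 82.3 | 82.1 | 83.3 | 86.6 | 4.3 |
| 1.25 | 0.2 (0.3) | 66.1 / 40.7 | 86.7 | 86.3 | 87.2 | 89.7 | 3.0 |
| 1.25 | 0.4 (0.5) | 61.2 / 36.2 | 83.2 | 83.6 | 84.2 | 88.7 | 5.5 |
| 1.5 | 0.2 (0.3) | 67.0 / 41.2 | 88.5 | 88.2 | 89.0 | 92.7 | 4.2 |
| 1.5 | 0.4 (0.5) | 61.5 / 36.1 | 86.0 | 86.6 | 86.8 | 91.5 | 5.5 |

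A separate run with mean rise 0.3 (2,000 trials per slope) gave gains of about 1, 2, 4 and 7 points at slopes 0.5, 0.8, 1.2 and 1.8. With slope zero (1,000 trials), power went from 75.9% to 77.1% and from 76.2% to 77.5%. About one point of the gain therefore comes from changing the test and not from the covariate.

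**Type I error.** At slopes 1.0 and 2.0 (1,000 null trials each), CMH on screening strata rejected in 4.1% and 4.8%, and the logistic test in 3.9% and 5.1%.

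**Which strata.** Screening and Day 1 values fell on opposite sides of 10,000 in 16% (smaller rise) and 26% (larger rise) of subjects, or about 23 to 37 of 141. Swapping the strata moved CMH power by at most 1 point in the table.

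**Perspective.** At the cited Week 2 response of 72% versus 9% (section 4.4), unadjusted power is essentially 100%. At 59% on BCV (section 4.3.3.1) against assumed SoC rates of 30%, 35%, 40% and 45%, it is 91%, 77%, 57% and 35%. The unknown SoC rate matters far more than the form of adjustment.

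**How steep is the slope?** Fixing the BCV rate at 59% overall, the model gives 68.3% (smaller rise) or 71.5% (larger rise) below 5 log10 at slope 1.25, and 71.2% or 75.7% at slope 2.0. Section 4.3.3.2 reports 72%, which would suggest 1.25 or more. However, the 59% covers HCT recipients still on study at Week 4, while the 72% is given for pediatric subjects below 5 log10. They are differently described groups, so the slope stays an assumption.

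**The case against.** The strongest reply is that CMH on the randomization factors is a recognised, pre-specified and valid test, and choosing logistic regression instead is a trade-off. The responder proportions are other secondary endpoints with no power target to miss. AAUC at Weeks 2, 4, 6 and 12 already keeps continuous viremia, so early virologic response has an efficient analysis. The cut at 10,000 has some support in the protocol's background, since the quick clearance is reported for children below it. With a 9% SoC response, 0.09 × 47 ≈ 4 SoC responders would be expected at Week 2, where an ordinary logistic fit can be unstable. Sections 6.1 and 8.8 make the screening value the most natural reading of 12.4.2, and section 12 leaves detail to the SAP. The document reviewed holds no separate SAP text that could settle the matter.

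All of this stands, and it limits the point to an inexpensive improvement. It does not remove the contradiction in 12.4.1, and it does not explain why a gain in power wanted for the primary endpoint is passed over for responder endpoints when the Day 1 value is already collected.

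Three stronger readings are not supported. A reader might infer that the CMH tests are invalid or inflate error, but simulated rejection under the null was between 4% and 5%. A reader might infer that most of the effect of viremia goes unadjusted, but this is not shown, and CMH also stratifies on the other two factors. A reader might infer that the two strata definitions would yield materially different tests, but average power barely moves. That part is a matter of pre-specification.

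**Conclusion.** The contradiction is established from the text alone: the synopsis and section 12.4.1 misname the stratifier, and the strata used elsewhere are ambiguous as a result. About 20% of children would be classified differently, which rests on assumed viremia distributions, with power changing by about 1 to 2 points at most.

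The efficiency loss is real in direction and modest in size: roughly 1 to 4 points at slopes of 0.5 to 1.2, reaching 5 to 6 where screening and Day 1 values agree less well, about 7 at slope 1.8, and practically none at 72% versus 9%. These figures depend on the assumed slope, rise and responder rates, none of which the documents fix.

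**What to change.** - In the synopsis and section 12.4.1, say that the randomization factor is the last screening viremia before Day 1, and that continuous Day 1 log10 viremia is the covariate used in its place in the ANCOVA.
- In sections 12.4.1, 12.4.2 and 12.9, state that the CMH, pairwise and subgroup strata are those recorded by the IV/WRS at randomization.
- For the undetectable and 1- or 2-log10 decline endpoints, pre-specify logistic regression on treatment, T cell-depletion method, time from HCT and continuous Day 1 log10 viremia. Report a standardized risk difference with the odds ratio, name a penalized fit for use when responders are sparse, and keep CMH as supportive.

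The cost is protocol and SAP wording, with no added subjects, samples or visits. The downside is that the logistic odds ratio is conditional and will differ from the CMH common odds ratio, which is why the risk difference should be reported beside it. Sparse early time points may need the penalized fit.

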The study will also provide a holistic assessment of safety that includes the known side effects of oral BCV (GI toxicity) and IV CDV (renal injury). Immunosuppressant therapies utilized in the study will be recorded to document that short course BCV therapy and updated safety management guidance has mitigated the overuse of steroids observed in the CMX001-301 study (Section 4.2.3.1). Though it is anticipated that control of AdV replication will limit resulting organ damage and numerically improve survival in patients treated with oral BCV, a non-inferiority analysis of overall mortality at Week 16 between the BCV and SoC arms is included as a key secondary efficacy endpoint in order to rule out an untoward effect of BCV on outcomes.

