5.3. Secondary and Exploratory Endpoints

5.3.1. Key Secondary Efficacy Endpoint

The key secondary efficacy endpoint is the incidence of all-cause mortality through Week 16.

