- Multiple imputation, where the missing part of the trajectory is imputed based on a model ([Rubin 1978](#)). This imputation is repeated to create multiple simulated data sets (e.g., 5-times the number of deaths plus drop-outs). Each of these simulated data sets is analyzed independently and the results from these analyses are pooled to yield a final inference.
- Undetectable imputation, where the missing part of the trajectory is imputed as undetectable.

In addition to the above, three other supportive analyses are proposed to directly account for subjects who die prior to Week 16:

- Baseline imputation, where the missing part of the trajectory for deaths only is imputed at the baseline value for the subject.
- Analysis of time below the detection limit, whereby subjects who die are considered to be above the detection limit after death. This approach will be repeated using time below 1000 copies/mL, which is a clinically-meaningful level of viremia often signaling viral control vs. need to address in clinical practice.
- Generalized pairwise comparisons of prioritized outcomes ([Buyse 2010](#)). In this approach, all BCV subjects are compared with all SoC subjects in the same stratum. Comparisons will be made based on the following hierarchy:
 - Alive or dead at Week 16
 - If both die before Week 16, compare time to death
 - If both are alive at Week 16, compare AAUC

Each comparison yields a favorable, unfavorable, or neutral result. The “proportion in favor of treatment” (Δ) is the net difference between the number of favorable pairs and the number of unfavorable pairs divided by the total number of pairs. The null hypothesis $H_0: \Delta=0$ is tested using a randomization test.

Another important factor that may influence the primary inference is the imputation of undetectable and BLQ AdV viremia values, with additional sensitivity analyses conducted in order to assess the potential impact of this imputation:

- Impute all undetectable/BLQ values at 1 copy/mL (i.e., 0 log₁₀ c/mL)
- Impute all undetectable/BLQ values at 189 copies/mL
- Impute all values < 1000 copies/mL at 1 copy/mL

In addition, a supportive analysis of overall mortality (adjusting for advanced baseline disease, [Matthes-Martin 2008](#)) will examine the non-inferiority of BCV treatment to SoC. No negative impact on mortality will be concluded if the upper bound of the one-sided 95% confidence

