interval (CI) for the absolute difference between BCV mortality and SoC mortality is $< 10\%$. The proposed sample size will have $> 80\%$ power to demonstrate this conclusion, assuming SoC mortality in the expected range of 20% to 30% and a risk difference of 6% to 9% in favor of BCV (Feghoul 2015, Hiwarkar 2017, Mynarek 2014). In the event this supportive analysis concludes non-inferiority and the primary endpoint is met, superiority for overall mortality at Week 16 will be tested at alpha 0.05. Non-relapse mortality will be assessed in a similar fashion.

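### The only missing-data rule stated for binary secondary endpoints counts unknown vital status as death, with no exception for the Week 16 mortality non-inferiority test; excess loss on SoC would then favour BCV

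*Combined protocol and SAP*

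**What the plan says.** Section 12.4.2 and the synopsis (Statistical Methods) give one rule for dichotomous secondary efficacy analyses: "Missing data will be imputed as failure". No endpoint is excepted. For time-to-event analyses Section 12.4.2 has a different rule: "Missing data will be censored, generally at the earlier of the end of study for each subject" or the analysis time point.

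Section 5.3.1 states: "The key secondary efficacy endpoint is the incidence of all-cause mortality through Week 16". Section 4.3.7 says that "a non-inferiority analysis of overall mortality at Week 16 between the BCV and SoC arms is included as a key secondary efficacy endpoint", included to rule out harm from BCV.

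The test itself is set out in Section 12.4.1, where it is called supportive and is adjusted for advanced baseline disease. Non-inferiority is concluded if the "upper bound of the one-sided 95% confidence" interval for BCV minus SoC mortality lies below 10 percentage points. If it does, and the primary endpoint is met, mortality superiority is tested next. Neither paragraph says how unknown vital status is handled. Section 12.2 analyses efficacy in all randomised subjects, so lost subjects stay in the denominator.

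**The concern.** Counting missing as failure is a cautious choice when success is a virologic response and the aim is superiority. It is not reliably cautious for a mortality non-inferiority test, because an imputed control death lowers the estimated excess on the test drug. With 2:1 allocation the SoC arm has 47 subjects, so each imputed SoC death counts twice as much as one on BCV. The superiority test that follows would inherit the same data.

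At stake is the comparison meant to detect a harmful effect of BCV on survival. Section 4.2.3.1 reports numerically higher mortality on BCV in an earlier trial, so this test should not become easier to pass because subjects are lost.

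**Working it through.** **Inputs.** 94 BCV and 47 SoC (synopsis); margin 10 points, one-sided 95% bound (12.4.1); planning rates, "assuming SoC mortality in the expected range of 20% to 30% and a risk difference of 6% to 9% in favor of BCV" (12.4.1). The protocol gives no loss rate, so the loss counts below are assumptions.

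**1. The plan's own figure.** The planned pairs are SoC 20% with BCV 14%, and SoC 30% with BCV 21%. Overall mortality is (94×0.14 + 47×0.20)/141 = 16% and (94×0.21 + 47×0.30)/141 = 24%, matching the 16% to 24% in Section 12.4.1. Non-inferiority power with the Farrington-Manning variance is 79.8% and 80.9%. Exact enumeration of the simple unpooled (Wald) rule gives 78.5% and 78.9%. The stated power of more than 80% is therefore reproduced to within about 2 points, and the set-up is the intended one.

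**2. Shift per lost subject.** Counting one subject dead instead of alive moves the difference by 1/47 = 2.1 points toward BCV (SoC loss) or 1/94 = 1.1 points away from BCV (BCV loss).

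**3. A borderline example.** Upper bound = pB − pS + 1.645 × √[pB(1−pB)/94 + pS(1−pS)/nS]. Take 18/94 deaths on BCV, 9 known deaths on SoC, and one SoC subject lost.

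| Handling of the lost SoC subject | SoC deaths | Difference | SE | Upper bound | Non-inferior? |
|---|---|---|---|---|---|
| Counted dead | 10/47 | −2.13 | 7.22 | 9.75 | yes |
| Counted alive | 9/47 | 0.00 | 7.03 | 11.56 | no |
| Excluded | 9/46 | −0.42 | 7.12 | 11.29 | no |

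If two BCV subjects are also lost and counted dead (20/94 against 10/47), the bound is 12.03 and the test fails.

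**4. False-pass rate when BCV is truly 10 points worse.** Exact binomial enumeration over all outcomes, with the stated number of lost subjects fixed as deaths and the Wald bound compared with 10 points:

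| Losses counted as deaths (SoC / BCV) | SoC 20%, BCV 30% | SoC 25%, BCV 35% |
|---|---|---|
| 0 / 0 | 4.4% | 4.6% |
| 1 / 0 | 6.5% | 6.5% |
| 2 / 0 | 9.5% | 9.2% |
| 3 / 0 | 13.4% | 12.5% |
| 1 / 2 | 4.2% | 4.5% |
| 2 / 4 | 4.0% | 4.4% |
| 3 / 6 | 3.9% | 4.3% |

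At SoC 20%, losses on BCV only (1, 2, 3) give 3.5%, 2.7% and 2.1%.

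**5. Losses at random.** If each subject is lost with a fixed probability instead, 5% loss in both arms changes the true risks at SoC 20% to 0.30 + 0.70×0.05 = 33.5% and 0.20 + 0.80×0.05 = 24.0%. The difference shrinks to 9.5 points and the false-pass rate is 5.2%. With 5% loss on SoC only it is 11.9%. The pattern is the same: little change under equal loss, clear inflation under excess SoC loss.

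**The case against.** **Scope.** The missing-as-failure sentence closes a paragraph on Cochran-Mantel-Haenszel tests and odds ratios. The non-inferiority test sits in another section, on a risk-difference scale, with a different adjustment, and failure is never defined for mortality. That the rule governs the test is an inference across sections. This stands. But Sections 4.3.7 and 5.3.1 place the mortality comparison among the secondary endpoints, and no other rule is stated. If the rule was not meant to apply, the non-inferiority test has no missing-data rule, which needs the same repair. Section 12 leaves detail to the SAP, so the repair can be made there.

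**Symmetry.** A lost BCV subject is also counted dead and counts against BCV. This stands fully: proportional losses leave the error rate near or below its level without losses, or slightly above 5% under random loss.

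**Likelihood.** A reader might infer that withdrawal will be more common on SoC because treatment is open-label (8.8) and SoC subjects cannot receive BCV before Week 16 (8.5). The documents do not support more than a possibility. They give no loss rate by arm, keep all randomised subjects in follow-up to Week 36 (7.3), and expect almost no loss (12.4.1). Access to BCV after the Week 16 assessment could equally encourage staying.

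**Contradiction.** A reader might also say that the incidence and time-to-death analyses contradict each other because one imputes and the other censors. They are different conventions for different summaries. The time-to-death analysis offers a view free of imputed deaths, although it does not test the 10-point margin.

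**Conclusion.** The gap is real and conditional. As written, the only rule that reaches binary mortality counts unknown vital status as death. If loss is proportionally higher on SoC, the false-pass rate at a true 10-point excess rises from about 4.5% to about 6.5%, 9% and 13% with one, two and three SoC-only losses. With losses proportional to allocation it stays at 3.9% to 4.5%. It would be too strong to say that the rule favours BCV in general, or that one withdrawal will decide the result: the example in the working turns on a single subject only because it lies close to the margin.

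The figures assume SoC mortality of 20% to 25% and an unadjusted Wald bound. The plan adjusts for advanced baseline disease and does not name its interval method, so they show direction and approximate size. The sensitivity analyses listed in Section 12.4.1 concern AAUC and do not vary unknown vital status in the margin test.

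**What to change.** State in the SAP, before the primary database lock:

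- Missing-as-failure applies to virologic and other response endpoints, not to mortality.
- For the mortality non-inferiority and superiority comparisons, estimate the Week 16 risk difference by Kaplan-Meier, censoring at the date last known alive, stratified or standardised by advanced baseline disease so that the planned adjustment is kept.
- Add a worst-case or tipping-point check, with missing BCV subjects dead and missing SoC subjects alive at the extreme. This is needed because censoring assumes that loss is unrelated to prognosis, which is doubtful in the very situation of concern.

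The cost is SAP wording and a little programming. Non-inferiority becomes slightly harder to reach if SoC subjects are lost. With complete vital status the choice of missing-data rule has no effect.
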